9.5 Safety and Tolerability Analysis

Demographic parameters will be summarized descriptively.

Safety and tolerability analysis will be performed for all subjects in the safety population. No inferential statistical analysis of safety data is planned.

Safety and tolerability of AIO-001 will be evaluated through the assessment of AEs (i.e., seriousness, severity, relationship to the study drug, outcome, duration, and management), vital signs, 12-lead ECGs, clinical laboratory tests, and physical examinations. AEs will be coded using the latest version of the Medical Dictionary for Regulatory Activities (MedDRA).

TEAEs will be tabulated by treatment. Changes from baseline values in vital signs, 12-lead ECGs, and clinical laboratory tests will be evaluated. Safety and tolerability data will be reported using descriptive statistics.

9.5.1 Interim Analyses

Interim analyses of preliminary data will be performed at Sponsor discretion.

10. Data Collection

The electronic source data capture system is the primary data collection instrument for the study. Collection screen in the electronic source data capture system will be utilized for the collection of all data. Data will be entered using the English language and should be kept current to enable the monitor to review the subjects' status throughout the course of the study.

Source data should be attributable, legible, contemporaneous, original, accurate, and complete. Source documents will be maintained in order to maintain data integrity. The Investigator and/or the clinical staff have the responsibility of ensuring the accuracy, completeness, legibility, and timeliness of the source data.

Details on the data management process will be described in a data management plan (DMP).

11. Regulatory Considerations and Quality Assurance

11.1 IEC Approval of Protocol and Other Study Documents

The Investigator(s) agree to provide the IEC with all appropriate documents, including a copy of the protocol/amendments, ICFs, advertising text (if any), Investigator's Brochure (if any), and any other written information provided to study subjects. The trial will not begin until the Investigators have obtained the IEC favourable written approvals for the above-mentioned study documents. A properly executed written ICF shall be read, signed, and dated by each subject prior to entering the trial or prior to performing any study procedure. The original signed and dated ICF will be kept at the clinical site and a copy will be given to the subject.

In the event that the protocol is amended, the revised protocol must be approved by the IEC prior to its implementation, unless the changes involve only logistical or administrative aspects of the trial. If a revised ICF is introduced during the study, each subject's further consent must be obtained. The new version of the ICF must be approved by the IEC, prior to subsequently obtaining each subject's consent.

The Investigator and the Sponsor's representative must sign the protocol and its amendments (if any) before initiating the study.

It is the Sponsor's responsibility to submit the protocol and its amendments (if any), and the ICFs to regulatory authorities when necessary.

11.2 Compliance

This study will be conducted in compliance with the protocol, GCP, the requirements of Directive 2001/83/EC Annex I, as amended by Directive 2003/63/EC and Directive 2001/20/EC, and all applicable regulations, including the Federal Food, Drug and Cosmetic Act, U.S. applicable Code of Federal Regulations (title 21), and any IEC requirements relative to clinical studies. The study will also be conducted in compliance with the recommendations laid down in the most recent version of the Declaration of Helsinki, with the exception that registration of such Phase 1 trials in a publicly accessible database is not mandatory.

11.3 Quality Assurance and Monitoring

The Sponsor or its designee will perform the quality assurance and quality control activities of this study; however, responsibility for the accuracy, completeness, security, and reliability of the study data presented to the Sponsor lies with the Investigator generating the data. When applicable, quality assurance procedures will be performed according to the site SOPs.

The study will be monitored according to the site monitoring plan and SOP to ensure that it is conducted and documented properly according to the protocol, GCP, and all applicable regulatory requirements. The Sponsor is entitled to access information about the status of the study and to review the original documents of the study.

The Sponsor may arrange audits as part of the implementation of quality assurance to ensure that the study is being conducted in compliance with the protocol, SOPs, GCP, and all applicable

regulatory requirements. In such case, audits will be independent of and separate from the routine monitoring and quality control functions.

K _{el}	terminal elimination rate constant
K _{el} lower	lower terminal elimination rate constant
K _{el} upper	upper terminal elimination rate constant
Ln	natural logarithm
LS	least squares
max	maximum
MedDRA®	Medical Dictionary for Regulatory Activities
min	minimum
N	number of subjects
n	number of observations
N/A	not applicable
PK	pharmacokinetic(s)
PT	preferred term
p-value	probability value
R ²	R-squared

This document is confidential.

Abbreviation	Description
SAP	statistical analysis plan
SC	subcutaneous
SD	standard deviation
SOC	system organ class
SOP	standard operating procedure
T _{1/2 el}	terminal elimination half-life
TBD	to be determined
TEAE	treatment-emergent adverse event
TFLs	tables, figures, and listings
T _{max}	time of maximum observed concentration
T _{½.}	terminal elimination half-life
vs	versus
WHODrug	World Health Organization Global Drug Dictionary

This document is confidential.

1. Purpose

The purpose of this statistical analysis plan (SAP) is to ensure that the data listings, summary tables, and figures which will be produced, and the statistical methodologies that will be used, are complete and appropriate to allow valid conclusions regarding the study objectives.

This SAP is based on the following documents:

- Protocol AIO-001-101 2.0, dated 29 Nov 2023
- Electronic case report form (eCRF) version 3.0, dated 04 Mar 2024

The plan may change due to unforeseen circumstances; any changes made after the plan has been finalized will be documented in the associated clinical study report (CSR). No revision to the SAP is required for changes which do not affect the statistical analysis methods, definitions, or rules defined in this document. If additional analyses are required to supplement the planned analyses described in the SAP, the changes and justification for the changes will be outlined in the associated (CSR). No change will be made without prior approval of the Sponsor.

When applicable, all methodologies and related processes will be conducted according to Syneos Health's standard operating procedures (SOPs), as appropriate. Shells for all statistical tables, listings, and figures referred to in this SAP will be presented in a separate document.

1.1 Responsibilities

Syneos Health will perform the statistical analyses and are responsible for the production and quality control of all tables, figures, and listings (TFLs).

1.2 Timings of Analyses

Interim Analysis

An interim analysis will be performed at the end of 12 weeks, after all subjects complete Day 85, safety, tolerability, pharmacokinetic (PK), and immunogenicity data will be analyzed for primary and secondary endpoints for an interim report

Final Analysis

The final safety, tolerability, PK, and immunogenicity analysis will be completed after all subjects complete the final study visit or terminate early from the study.

This document is confidential.

2. Study Objectives

- Primary objective:
 - To compare the safety and tolerability of 400 mg of AIO-001 as the new formulation (Formulation B) with a 400 mg dose of AIO-001 administered as the original formulation (Formulation A) in healthy volunteers.
- Secondary Objectives:
 - To evaluate the PK of a single subcutaneous (SC) AIO-001 dose of Formulation A in healthy volunteers.
 - To evaluate the PK of a single SC AIO-001 dose of Formulation B in healthy volunteers.
 - To evaluate the immunogenicity of AIO-001 in healthy volunteers.

3. Study Description

This is an open-label single dose, parallel group, 24-weeks, Phase 1 study in 16 healthy subjects.

The study is designed to evaluate and compare the safety, tolerability, PK, and immunogenicity of SC AIO-001 400 mg using two different formulations (original Formulation A and new Formulation B) in 16 healthy volunteers (8 receiving each formulation).

Subject Selection

Up to approximately 16 healthy adult males or females aged 18 to 55 years, with body mass index (BMI) >18.5 and <32.0 kg/m², non-smokers, will be enrolled in this study.

3.1 Determination of Sample Size

The proposed number of subjects is in line with the sample sizes commonly used in clinical studies of this nature and is considered sufficient to achieve the study objectives. No formal sample size calculation was performed for this Phase 1 study.

3.2 Treatment Assignment

Sixteen healthy volunteers (8 receiving each formulation) will receive one of the following treatments, according to the randomization scheme. The planned dose levels are listed in [Table 3.3-1](#), below.

Table 3.3-1: Treatments

Group	Number of Subjects	Treatments	Planned Dose
A	8	AIO-001 as Formulation A	400 mg of 100 mg/ml, given as 4 X 1.0 ml
B	8	AIO-001 as Formulation B	400 mg of 182 mg/ml, given as 2 X 1.1 ml

This document is confidential.

3.3 Randomization

Randomization schemes will be generated using SAS® for Windows software, prior to study execution.

Subjects will be randomized prior to dosing, after confirming continued eligibility. Subjects eligible for participation will be randomized to receive formulation A or formulation B in a 1:1 ratio, for a total of 8 subjects receiving formulation A and 8 subjects receiving formulation B.

The study will include 2 sentinel subjects (1 for each treatment) dosed initially, and the remaining 14 subjects dosed no sooner than 24 hours.

Each subject will be randomly assigned a 4-digit randomization number beginning with “1”. Each randomization number corresponds to a treatment assignment on the randomization scheme. Sentinel subjects will be assigned to the first 2 randomization numbers (i.e., 1001, 1002).

3.4 Blinding

This is an open-label study; blinding is not applicable.

3.5 Subject Withdrawal and Replacement

Subjects will be advised that they are free to withdraw from the study at any time. Over the course of the study, the Sponsor and the Investigator or designee may withdraw any subject from the study for one of the reasons described below; subject withdrawal will be done in accordance with the local guidance at the clinical site:

- Safety reason;
- Non-compliance with protocol requirements;
- Significant protocol deviation;
- Positive pregnancy test, drug screen or alcohol breath test.

Subjects who withdraw prior to dosing may be replaced automatically. In the event that the number of dropouts exceeds initial expectations, subjects who withdraw or are withdrawn from the study after dosing, for reasons other than safety and tolerability, may be replaced after consultation between the Investigator and the Sponsor. In such case, the total number of subjects dosed will remain within a maximum of 10 subjects for groups A and B.

4. Endpoints

- Primary Endpoints:
 - Adverse events (AEs), vital sign measurements (blood pressure, heart rate, respiratory rate, and tympanic temperature), 12-lead electrocardiogram (ECG) recordings, physical examinations, and clinical laboratory test results, including hematology, biochemistry, and urinalysis.
- Secondary Endpoints:
 - PK endpoints may include but are not limited to AIO-001 concentrations, AUC_{0-last}, AUC_{0-inf}, C_{max}, T_{max}, T_{1/2}.

This document is confidential.

- Incidence of anti-drug antibody (ADA) to AIO-001.

Analysis Populations

All subjects' inclusion status into each analysis population will be determined after database lock. Subjects will be analyzed according to the treatment received.

4.1 Randomized Population

The randomized population will include all randomized subjects. The randomized population will be used for subject listings.

4.2 Safety Population

The safety population is defined as all subjects who receive at least one dose of the study drug.

4.3 Pharmacokinetic Population

The PK population will include all subjects who have at least 1 measured PK concentration following dosing. If any participants have incomplete data, protocol deviations, or clinical events that affect PK, a decision will be made on a case-by-case basis as to their inclusion in the analysis. Before the final analysis, the Pharmacokineticist, in agreement with the Sponsor, will make the final decision of which subjects will be included in the PK populations, based on the datasets received.

4.3.1 Pharmacokinetic (PK) Concentration Population

The PK concentration population will include all subjects who receive AIO-001 and have at least one quantifiable post-dose PK concentration. The PK concentration population will be used for all PK concentration summaries and analyses.

4.3.2 Pharmacokinetic (PK) Parameter Population

The PK parameters population will include all subjects who receive AIO-001 and have sufficient post-dose concentration data to support accurate estimation of at least one PK parameter. The PK parameters population will be used for all PK parameter summaries and analyses.

4.4 Immunogenicity Population

The immunogenicity population will include all subjects who have received any amount of AIO-001 and have at least one post-dose ADA measurement.

5. General Aspects for Statistical Analysis

5.1 General Methods

SAS for Windows software will be used to perform all statistical analyses. All data in the database will be presented in the data listings. Unless otherwise stated, all listings will be sorted by treatment, subject number, and assessment date/time.

The following labels for treatment will be used on all tabulations where the results are displayed by treatment, in the following order:

- 400 mg of 100 mg/ml AIO-001 Formulation A

This document is confidential.

- 400 mg of 182 mg/ml AIO-001 Formulation B

5.2 Summary Statistics:

Unless otherwise stated, continuous variables will be summarized using the number of observations (n), and the statistics mean, median, standard deviation (SD), minimum (min) and maximum (max). The min and max values will be presented to the same number of decimal places as recorded in the eCRF, mean and median will be presented to one more decimal place than the raw data, and the SD will be presented to two more decimal places than the raw data.

Summaries of change from baseline variables will include only subjects who have both a baseline value and corresponding post baseline value at the timepoint of interest. Categorical and binary variables will be summarized with frequency counts and percentages. Percentages will be rounded to one decimal place, with the denominator being the number of subjects (N) in the relevant population, unless otherwise stated.

For PK data, values will be rounded to two decimal places in the listings and tables, except for the following situations:

- Terminal elimination rate constant (K_{el}) and R-squared (R^2) adjusted data shall be rounded off to four decimal places.
- PK parameters related to time, such as T_{max} , lower terminal elimination rate constant (K_{el_Lower}), and upper terminal elimination rate constant (K_{el_Upper}), must be reported with the same precision as the actual sampling time, rounded to three decimal places.
- Concentration versus time data, as well as C_{max} shall be reported as they appear in the corresponding dataset.
- Summary statistics, including geometric mean and coefficient of variation (CV%), will be presented to the number of decimal places is contingent on the number of places in the raw data plus one additional decimal place. The geometric mean and CV% will not be calculated for T_{max} , $T_{1/2}$, and K_{el} .

Only data from protocol scheduled (“nominal”) visits will be included in the summary tables. Data from unscheduled visits will not be included in the summary tables (unless they were used as baseline) but will be included in the listings and figures.

In the case of a repeat test, both assessments will be presented in the listings. If a repeat measurement was performed due to the first measurement being outside the normal range for the given assessment and the second assessment confirms the first measurement, then only the first measurement will be used for analysis and the second assessment will be considered an unscheduled timepoint. In the same case, if the second assessment falls within normal ranges, then the second assessment will be used for analysis of that timepoint. In all other cases, the first measurement will be taken as the assessment to be used for the analysis.

This document is confidential.

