9.1 Laboratory Evaluations

Laboratory data, including hematology, biochemistry, coagulation, and urinalysis (quantitative and categorical), will be listed by subject, and summarized by treatment and visit, categorical values less than x or greater than x will be summarized by frequency. Observed values and changes from baseline will be presented.

In addition, a shift table representing the categorical change (normal, abnormal not clinically significant, or abnormal clinically significant) from baseline to each post baseline visit will be presented by treatment.

Abnormal results will be flagged in the listings.

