9.2 Vital Signs

Vital sign measurements will be listed by subject and summarized by treatment, visit and timepoint. Observed values and changes from baseline will also be presented.

In addition, a shift table representing the categorical change (normal, abnormal not clinically significant, or abnormal clinically significant) from baseline to each post baseline visit and timepoint will be presented by treatment.

Abnormal results will be flagged in the listings.

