9.3 Electrocardiograms (ECGs)

Electrocardiogram (ECG) values will be listed by subject and summarized by treatment, visit and timepoint. Observed values and changes from baseline will be presented.

In addition, a shift table representing the categorical change in overall interpretation (normal, abnormal not clinically significant, or abnormal clinically significant) from baseline to each post baseline visit and timepoint will be presented by treatment.

Abnormal results will be flagged in the listings.

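### SAP 5.2 lets an in-range repeat replace an out-of-range post-dose reading but never the reverse, so by-visit safety tables can only show as many or fewer abnormal values than first readings

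*SAP*

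**What the plan says.** SAP 5.2 (Summary Statistics) sets the rule for a test repeated because the first value was outside the normal range.

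- If the repeat confirms the first value, the first value is analysed and "the second assessment will be considered an unscheduled timepoint".
- If the repeat is in range, the repeat takes over: "if the second assessment falls within normal ranges, then the second assessment will be used for analysis of that timepoint".
- The rule then closes: "In all other cases, the first measurement will be taken as the assessment to be used for the analysis".

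The same section keeps unscheduled data out of the summary tables unless used as baseline, and puts both readings of a repeated test in the listings.

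The selected values feed the by-treatment safety tables. SAP 9.1 (Laboratory Evaluations) plans a "shift table representing the categorical change (normal, abnormal not clinically significant, or abnormal clinically significant) from baseline to each post baseline visit". The SAP section on vital signs plans the same categories by visit and timepoint. Both sections, and the ECG section, also tabulate observed values and changes from baseline. For ECGs the categorical table is "a shift table representing the categorical change in overall interpretation".

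Protocol 8.2 leaves post-dose repeats to local site guidance or a request from the investigator or designee. SAP 3.4 confirms that the study is open-label.

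**The concern.** Laboratory results, vital signs and ECGs are among the primary endpoints, and SAP section 9 plans no inferential safety analysis. The descriptive tables are therefore an important part of the formulation comparison. A rule that can remove an abnormal value from them but cannot add one pushes every affected count in one direction.

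The rule does not ask whether the first reading was wrong. A haemolysed sample and a genuine transient change that has resolved by the time of the repeat are treated alike, and values judged clinically significant are not exempt. With 8 subjects per arm, one replaced value moves a shift-table cell by 1/8 = 12.5 percentage points. It can also pull an out-of-range minimum or maximum inward.

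**Working it through.** The documents give no figure on this point, so there is nothing to reproduce. The check has two parts: the logic of the rule, which needs no assumptions, and an illustration of size, which rests entirely on them.

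**Direction.** Take the first reading as in range, low or high; the repeat as absent, in range, low or high; and the reason for repeating as an out-of-range first value or something else. That gives 18 distinct cases.

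| First reading | Repeat | Reason for repeat | Cases | Value analysed | Change in abnormal count |
|---|---|---|---|---|---|
| In range | None, in range, low or high | Other | 4 | First | 0 |
| Low or high | None | n/a | 2 | First | 0 |
| Low or high | Low or high | Out of range | 4 | First | 0 |
| Low or high | In range | Out of range | 2 | Repeat | -1 |
| Low or high | Any | Other | 6 | First | 0 |

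Two cases turn abnormal into normal, none turns normal into abnormal, and 16 are unchanged. A repeat out of range on the opposite side is not addressed explicitly, but the first value is used on either reading of the rule.

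**Reach.** Two points in the text limit this.
- The ECG shift table uses overall interpretation, whereas the trigger is a value outside the normal range. The rule may therefore reach only the numeric ECG summaries.
- Unscheduled visits are kept out of the tables, so substitution may be confined to repeats within a scheduled visit.

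**Size, illustration only.** Every input here is assumed: two readings bivariate normal with SD 1, a 95% reference range of ±1.96, correlation 0.5 to 0.9 between first reading and repeat, and a fraction f of out-of-range values repeated once and eligible for substitution. One arm has mean 0 (unaffected) and the other mean +1 SD (shifted).

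- p = chance that the first reading is outside: 5.00% unaffected, 17.01% shifted.
- b = chance that both readings are outside (correlation 0.5 to 0.9): 0.93 to 2.96% unaffected, 6.83 to 12.43% shifted.
- Tabulated rate = p - f(p - b). For example, with f = 0.1 and correlation 0.5: 5.00 - 0.1 × (5.00 - 0.93) = 4.59%.
- Chance of at least one abnormal among 8 subjects = 1 - (1 - rate)^8.

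| f | Rate, unaffected | Rate, shifted | At least one of 8, unaffected | At least one of 8, shifted |
|---|---|---|---|---|
| 0 (first readings) | 5.0% | 17.0% | 33.7% | 77.5% |
| 0.10 | 4.6-4.8% | 16.0-16.6% | 31-33% | 75-77% |
| 0.25 | 4.0-4.5% | 14.5-15.9% | 28-31% | 71-75% |
| 0.50 | 3.0-4.0% | 11.9-14.7% | 21-28% | 64-72% |
| 1.00 | 0.9-3.0% | 6.8-12.4% | 7-21% | 43-65% |

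At f = 0.1 the expected loss in an unaffected arm of 8 is 8 × (0.0500 - 0.0459) = 0.03 subjects at most and 8 × (0.0500 - 0.0480) = 0.02 at least, per visit and test. At a correlation of 0.95 the unaffected rate is 4.3% with half repeated and 3.5% with all repeated.

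**Unequal repeating.** The ratio of first-reading rates is 17.01/5.00 = 3.4. If half of the out-of-range values are repeated in both arms, it becomes 14.72/3.98 = 3.7 to 11.92/2.96 = 4.0. If 10% are repeated in the unaffected arm and 50% in the shifted arm, it becomes 11.92/4.59 = 2.6 to 14.72/4.80 = 3.1. The effect on the comparison thus depends on whether the arms are repeated equally often.

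**The case against.** The strongest reply is that this is a confirmatory-repeat rule, fixed in advance and identical for both arms, and that it trades sensitivity for specificity. The illustration supports that. In the unaffected arm, the chance of at least one chance abnormality falls from 33.7% to 7-21% if everything is repeated. Where the two arms' counts differ, the chance that they point the right way is about the same or better: 86.6% with first readings against 86-91%. The price is that the shifted arm shows the higher count less often: 63.5% falls to 62-63% with 10% repeated and to 41-57% with all repeated. This objection stands as far as it goes. Preferring a first-value rule is partly a matter of judgement.

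Several stronger readings are tempting but not supported:

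- **That abnormal values are lost from the report.** Listings hold both readings and flag abnormal results, and with 16 subjects they can be read person by person. An abnormal laboratory finding can be recorded as an adverse event, and treatment-emergent event tables do not use this rule.
- **That these tables alone carry the safety comparison.** Adverse events are also a primary endpoint and are tabulated by severity and relationship.
- **That the tables will conceal a replacement.** The table shells are a separate document, and the SAP provides for footnotes and programming notes. The SAP text does not require a mark, but the shells may contain one.
- **That the rule favours one formulation, or that it must be neutral.** Neither follows. The wording is symmetric, but repeating is discretionary and treatment is known.
- **That SAP 5.2 and 5.3 conflict on baseline.** SAP 5.3 defines baseline explicitly, repeats included, and SAP 5.2 allows for unscheduled values used as baseline.

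**Conclusion.** The point holds for post-baseline by-visit summaries and shift tables. The analysed value is selected by its result, in one direction only, without any requirement that the first reading be invalid. Tabulated abnormal counts are therefore at or below the first-reading counts. They are equal if no out-of-range value is repeated or every repeat confirms. This needs no assumption beyond the SAP wording.

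The size cannot be settled from the documents, which give no out-of-range rate, repeat rate or within-subject correlation. It is small if few values are repeated and substantial only if a large share are repeated and eligible for substitution. No direction of bias between formulations can be claimed, nor can equal effect on the arms be assumed. This is a shortcoming in how primary-endpoint tables are built that can be corrected cheaply. It does not make the safety evaluation invalid.

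**What to change.** Two additions to the SAP would remove the one-way suppression from the tables while leaving the confirmatory rule in place:

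1. Add, by treatment, a baseline-to-worst-post-baseline shift summary for laboratory tests and vital signs. It should include first readings, repeats and unscheduled values, with a footnote that the result depends on how often a subject was tested.
2. In the by-visit tables, mark or count each value where an in-range repeat replaced an out-of-range first reading.

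Both use readings already collected and cost SAP wording and a little programming.

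Preferred where the data allow: extend the first-measurement default already in SAP 5.2 to this case, and use a repeat only when the first reading is documented as technically invalid. The documents do not show that a reason for invalidity is recorded for laboratory tests, vital signs or ECGs, so the eCRF must be checked first. The criterion also adds a judgement in an open-label study.

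The downsides should be accepted openly. Isolated out-of-range values that a repeat did not confirm will become visible, including chance ones in an unaffected arm. The worst-value summary leans toward abnormal in subjects tested more often.
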